**Table 6: Investigation: Renal**

Creatinine elevation management:			
Grade 1	All occurrences	Continue study drug	Maintain dose level
Grade 2	1 st occurrence	Interrupt study drug until resolved to Grade $\leq 1$ or baseline	Maintain dose level
	2 nd occurrence	Interrupt study drug until resolved to Grade $\leq 1$ or baseline	Restart at one lower dose level
	3 rd occurrence	Discontinue study drug	Not applicable
Grade 3	1st occurrence	Interrupt study drug until resolved to Grade $\leq 1$ or baseline	Restart at one lower dose level
	2nd occurrence	Discontinue study drug	Not applicable

Grade 4	Any occurrence	Discontinue study drug	Not applicable
---------	----------------	------------------------	----------------

**Table 7: Investigation: Coagulation**

INR management:			
Grade 1	All occurrences	Continue study drug	Maintain dose level
Grade 2	1 st occurrence	Interrupt study drug until resolved to Grade $\leq 1$ or baseline	Maintain dose level
	2 nd occurrence	Interrupt study drug until resolved to Grade $\leq 1$ or baseline	Restart at one lower dose level
	3 rd occurrence	Discontinue study drug	Not applicable
Grade $\geq 3$	Any occurrence	Discontinue study drug	Complete safety assessments as clinically indicated

#### 7.5.4. Safety Stopping Rules

Monitoring of all toxicity will be routinely performed by the SET-101 Safety Review Committee (SRC), composed of SET-101 investigators, Epizyme Medical Directors and Pharmacovigilance. Unacceptable toxicity is defined as those treatment-emergent adverse events that are at least possibly related to study drug, are of CTCAE Grade 4 or 5, and for which no other cause is identified.

For unacceptable toxicities: If there are more than 25% (of the total number of subjects treated within the safety population [MM and DLBCL]) study drug withdrawals due to treatment related grade 4 or 5 toxicity at any point during the study, the SRC will escalate the safety findings to an ad hoc Epizyme Quarterly Safety Review (QSR) committee meeting. The QSR committee, an internal cross functional scientific and medical review board, will determine the final action for study SET-101. The decision will be communicated to investigators and health authorities, as applicable.

For treatment related deaths: the SRC will also perform ongoing assessment and monitoring during routine data review meetings. All treatment-related deaths will trigger an ad hoc QSR meeting for full evaluation and decision with regard to continuing study SET-101.

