#### **Part 2: Phase 1b Safety and Efficacy Dose Expansion**

In the dose expansion phase, Bayesian optimal phase 2 (BOP2) design will be used to evaluate safety and efficacy in subjects with or without select genetic translocation in R/R MM and R/R DLBCL.

In the dose expansion part, 60 subjects will be enrolled (20 subjects/cohorts) and treated:

- Cohort 1: R/R MM with t(4;14)
- Cohort 2: R/R MM without t(4;14)
- Cohort 3: R/R DLBCL

During the treatment period, subjects will receive EZM0414 in continuous 28-day cycles. EZM0414 will be administered orally once daily (QD) without food (nothing to eat two hours prior and one hour after EZM0414 dose, water is permitted as needed). The subjects who receive EZM0414 at MTD and do not have DLT in the dose escalation part of the study will be rolled over to a cohort of this dose expansion part, depending on their condition (R/R MM or R/R DLBCL) and the select genetic translocation for R/R MM. All subjects will continue to receive treatment at the MTD in Phase 1b part until disease progression, occurrence of unacceptable toxicity, or withdrawal of consent, or need for treatment prohibited on this study. Subjects with R/R MM regardless of t(4;14) status will be enrolled first. Dose modifications for EZM0414 are discussed in [Table 4](#).

Safety assessments will be performed throughout the study and at each study visit. Vital signs including blood pressure, heart rate, respiration rate, and temperature will be collected according to schedule of assessments ([Table 8](#) and [Table 10](#)).

A single 12-lead ECG will be collected at screening and triplicate ECGs, 1-minute apart will be collected at time points mentioned in [Table 8](#) and [Table 10](#).

Blood samples will be collected from all subjects for PK analyses at the time points mentioned in [Table 10](#).

At time points where vital signs, ECG and PK blood samples are required, the following order of collection is recommended 1) vital signs, 2) ECG and 3) blood sample for PK analyses and biomarker analyses.

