## **7.5. Dose Adjustment Criteria**

### **7.5.1. Dose Limiting Toxicities**

Any adverse event (AE) which meets the criteria of a DLT as assessed by the Investigator and warrants action as per [Table 3](#), will be reviewed by the Safety Review Committee (SRC). No intra-patient dose reduction will be permitted in Cycle 1 of dose escalation. For subjects who require a dose interruption due to a DLT during cycle 1, the treatment will be restarted once the toxicity resolves to Grade  $\leq 1$  or baseline. However, an interruption in the administration of EJM0414, for more than 14 days will be discussed with the Sponsor's or Designee Medical

Monitor before treatment can be resumed. The DLT evaluable subjects will consist of dose escalation dose level subjects who received at least 80% of planned study treatment during cycle 1. If a subject is non evaluable, this subject will be replaced by a new subject.

Safety assessments will be performed throughout the study and at each visit. DLT period is 28 days of cycle 1 of the dose escalation part. AEs that are clearly and incontrovertibly due to the underlying disease or extraneous causes will not be considered as DLTs. All of the AEs of specified grades as listed in Table 3 will be classified as DLTs. Events will be assessed as DLTs according to the Common Terminology Criteria for Adverse Events (CTCAE 5.0), as shown in [Table 3 \(Appendix 5\)](#). When a subject is assessed to be experiencing a DLT, study treatment will be interrupted and DLTs will be managed by concomitant medication (as appropriate), treatment discontinuation, or a combination of these. All dose escalation decisions will be made by the SRC and Sponsor upon review of all available data. Determination of the MTD will be informed by all available data, including the overall tolerability of EZM0414.

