**Table 14: Total Daily Dose and Respective Dose Level**

Dose Level	Total Daily Dose (mg)
-1 (optional)	75
1	100
2	200
3	300
4	400
5	600
6	900

Additional daily dose levels and/or dosing schedules (including BID regimen) may be studied based on clinical and pharmacokinetic data obtained during this study.

Bayesian optimal interval design ([Liu, 2015; Yuan, 2016; Zhou, 2017](#)) will be used for this dose escalation part. Similar numbers of subjects with R/R MM or R/R DLBCL will be enrolled to determine MTD. The target toxicity rate ( $\varrho_T$ ) for the MTD is set at **0.25** for both R/R MM and R/R DLBCL. The maximum number of subjects for determination of MTD is 9. A total of 6 dose levels ( $j = 6$ , ie, starting at 100 mg, then 200 mg, 300 mg, 400 mg, 600 mg, and 900 mg) as well as an optional step-down dose level of 75 mg will be investigated. We will enroll and treat subjects in groups of at least 3, and up to 36 subjects will be enrolled in this dose-escalation part of the study in order to evaluate at least 9 subjects for MTD. Dose limiting toxicities are defined in Section [7.5.1](#), and only those DLTs that occur within the first cycle will be used for safety assessment. The BOIN design uses the following rules, optimized to minimize the probability of incorrect dose assignment, to guide dose escalation/de-escalation:

- if the observed DLT rate at the current dose is  $\leq 0.197$ , escalate the dose to the next higher dose level;
- if the observed DLT rate at the current dose is  $\geq 0.298$ , de-escalate the dose to the next lower dose level;

- otherwise, stay at the current dose.

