**Table 16: Optimized Stopping Boundaries for R/R MM Cohort**

Sample size for interim looks	Stop if # Response $\leq$
10	1
15	3
20	6

ORR = Objective response rate; R/R = Relapsed/refractory; MM = Multiple myeloma.  
 $H_0$ : ORR (Futile)=0.2;  $H_1$ : ORR (Promising)=0.35; Type I Error Rate=0.1

Based on [Table 16](#), futility assessments will be conducted for each R/R MM cohort when response assessment data become available (ie, minimum 5 cycles or if all subjects progressed) in the first 10 enrolled subjects, and again in the first 15 enrolled subjects. Enrolment will not cease during the assessment periods. When the response assessment data are available for the total number of 20 subjects, we reject the null hypothesis for the cohort and conclude that the treatment is promising (go) if the number of responses is more than 6 ( $>6$ ); otherwise, we conclude that the treatment is futile (no-go). The go/no-go criteria in [Table 16](#) are non-binding.

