## 14.3. Analysis Populations

**Safety Population:** Safety analyses will be composed of all subjects who receive at least 1 dose of the study drug in Phase 1 (dose escalation part) or Phase 1b (dose expansion part).

**Dose-limiting toxicity (DLT) Evaluable Population:** The DLT evaluable population will consist of dose escalation dose level subjects in the Safety Population who received at least 80% of planned study treatment during cycle 1.

**Intent-to-Treat (ITT) Population (Phase 1b Dose Expansion Portion):** The ITT Population is defined as all subjects enrolled in corresponding cohorts of Phase 1b part, regardless of their adherence with the entry criteria, the treatment they actually received, and subsequent withdrawal from treatment or deviation from the protocol. The ITT Population includes the subjects who received the study treatment at MTD in Phase 1, dose escalation part and are rolled over to the corresponding cohorts of the Phase 1b, dose expansion part.

**PK Analysis Population:** will include all subjects in the Safety Analysis population who have sufficient post-dose blood sample collected to allow estimation of the PK parameters.

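### The 25% withdrawal trigger pools all doses and both parts, so subjects dosed below the MTD can delay the mandatory ad hoc QSR meeting for non-fatal Grade 4 toxicity at the expansion dose

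*Protocol*

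**What the plan says.** Protocol Section 7.5.4 sets the denominator as the share "of the total number of subjects treated within the safety population" and the numerator as study drug withdrawals for "treatment related grade 4 or 5 toxicity at any point during the study". Above 25%, the Safety Review Committee (SRC) must take the findings to an ad hoc QSR meeting, which decides what happens to the study. Deaths have their own route: "All treatment-related deaths will trigger an ad hoc QSR meeting".

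Section 14.3 defines the Safety Population as "all subjects who receive at least 1 dose of the study drug in Phase 1" or Phase 1b. It sets no limit by dose level.

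Two other quantitative rules might have covered toxicity in expansion, but neither does:

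- The DLT rule ends with escalation. Section 7.5.1 states: "DLT period is 28 days of cycle 1 of the dose escalation part".
- Section 7.1 says that the BOP2 design "will be used to evaluate safety and efficacy in subjects" in expansion, but its boundaries in Tables 16 and 17 of Section 14.1 count responses only. For myeloma, "futility assessments will be conducted for each R/R MM cohort when response assessment data become available". Section 7.5.6 likewise provides for early closure of a cohort only for futility.

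**The concern.** Expansion treats everyone at one dose, the MTD. The question there is how often that dose forces patients off treatment with Grade 4 toxicity. The trigger answers a different question, because its denominator permanently includes everyone treated at lower doses in escalation. If few of them withdrew, the rate at the MTD must go well past 25% before the pooled figure does.

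What is at stake is the timing of one mandatory step, the out-of-schedule QSR meeting, when non-fatal Grade 4 toxicity at the MTD is too frequent. Events in escalation also count in the numerator, so dilution arises only while the escalation withdrawal rate is below 25%.

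**Working it through.** **The plan's own figures.** The protocol gives no operating characteristics for the 25% rule, so there is nothing to reproduce for it. The neighbouring rule that the fix borrows can be checked. With a uniform prior, the posterior after x events in n is Beta(1+x, 1+n−x). The smallest x with Pr(p > 0.25 | data) > 0.8 is 2, 2, 2, 3, 3, 3, 4 for n = 3 to 9, which matches the elimination row of Table 15.

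**Inputs from the protocol.** The threshold is more than 25% (Section 7.5.4). Escalation enrols up to 36 subjects "in order to evaluate at least 9 subjects for MTD", and expansion enrols 60 (Section 7.5.6).

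**Assumptions, because the documents give no withdrawal data or expected rate.** 24 escalation subjects, 9 of them at the MTD. 60 newly enrolled expansion subjects. Independent outcomes with true rate p at the MTD, and a check after every expansion subject. If rolled-over subjects count within the 60, fewer new subjects follow.

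**Rule.** With k events in total and n expansion subjects, it fires when k/(24+n) > 0.25.

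**By hand.** At n = 20 the denominator is 44 and 12 events are needed.

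- No escalation events: 12 of 20 expansion subjects (60%).
- 2 escalation events: 10 of 20 (50%).
- 4 escalation events: 8 of 20 (40%).

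If only MTD subjects have events, the expected pooled rate is p(9+n)/(24+n). At p = 0.30 and n = 60 this is 0.30 × 69/84 = 24.6%, still under the limit at full enrolment.

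**Exact recursion over n = 1 to 60.** The cases differ in escalation events:

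| Escalation events | Fired by subject 20, p = 40% | Median subject, p = 40% | Ever fires, p = 40% | Ever fires, p = 30% |
|---|---|---|---|---|
| (a) none in 24 | 9% | 38 | 82% | 26% |
| (b) 9 at MTD with at most 2; none in other 15 | 30% | 27 | 92% | 43% |
| (c) 9 at MTD share rate p; none in other 15 | 64% | 15 | 97% | 59% |
| (b) plus 2 events above the MTD | 67% | 14 | 98% | 70% |
| (c) plus 2 events above the MTD | 89% | 3 | 99% | 82% |

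Case (a) is extreme: at p = 0.40, no event among 9 has probability 0.6⁹ = 0.010. Case (b) reflects Table 15, which de-escalates at 3 or more DLTs in 9, although a DLT is not the same as a Grade 4 withdrawal.

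Escalation size matters as well. In case (c) at 40%, the probability of firing by subject 20 is 85% with 18 escalation subjects and 20% with 36.

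**Like for like.** Compare the rules when 20 subjects have been treated at the MTD (9 from escalation plus 11 new), at p = 0.40. In case (c) the pooled rule has fired with probability 43%. A single look requiring 7 of 20 fires with probability P(X ≥ 7) = 75% for X ~ Binomial(20, 0.40). With 2 events above the MTD, the same recursion gives the pooled rule 79%, and the added look gains nothing.

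**The case against.** The strongest reply is that escalation often overshoots. BOIN may find the MTD by dosing above it and coming back down, and events at those doses enter the numerator for good. The last two table rows show that just 2 such events remove much of the delay. This stands. It limits the size of the point, although it does not help if the top dose, 900 mg, becomes the MTD, or if the DLTs above the MTD are not Grade 4 withdrawals.

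Sections 14.2 and 14.4 generally treat the two parts separately, which might suggest that the trigger does too. But those sections govern analysis and presentation. Section 7.5.4 refers to the total treated and to any point in the study, and Section 14.3 spans both parts. The pooled reading is the natural one.

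A reader might infer that expansion has no protection against toxicity. The documents do not support that. The SRC reviews toxicity routinely and is involved in the looks at 10, 15 and 20 subjects per cohort (Section 7.5.6). Grade 4 events are SAEs (Section 13.2.5), reported within 24 hours (Section 13.4). Table 4 takes the individual off drug at a related Grade 4 event. Any treatment-related death prompts a QSR meeting. The sponsor may stop for medical reasons at any time (Section 7.6), and nothing bars the SRC from going to the QSR early. However, these safeguards act on single events or by discretion. None sets a rate at the expansion dose that obliges referral.

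Finally, a study-level denominator is defensible for a study-level decision. That is a reason to keep the pooled rule, not a reason to have no rule for the MTD.

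**Conclusion.** The point holds as a limited weakness in a backstop. Section 7.5.4 pools over dose and part, no other numerical toxicity-rate rule applies in expansion, and a low escalation withdrawal rate can therefore delay the mandatory ad hoc QSR meeting. Under the assumptions above, at a true 40% rate, the probability that the meeting has been triggered by expansion subject 20 is 30% to 64% if doses other than the MTD had no events. It is 67% to 89% with 2 events above the MTD. The direction is certain only when the escalation rate is below 25%; the size depends on enrolment and events that the documents do not give.

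It would go too far to say that the rule could not fire, that it always dilutes, or that QSR oversight as a whole is delayed. Only the ad hoc meeting depends on this threshold. The committee's name suggests a regular quarterly schedule, though the protocol does not say that this study is reviewed each quarter.

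SAP Section 1 records that the study ended during escalation on a business decision, and SAP Section 6.2 lists three dose levels conducted. The finding concerns the plan as written and any reuse of the rule.

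**What to change.** Keep the pooled 25% rule, the any-death trigger and the QSR process. Add to Section 7.5.4 an ad hoc QSR review based on subjects of both parts treated at the MTD, using the cut-off that Section 14.1 already applies per dose: Pr(p > 0.25 | data) > 0.8 with a uniform prior. The smallest counts that pass are:

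- 7 or more of 20 (posterior 0.870; 6 gives 0.744)
- 13 or more of 40 (0.878; 12 gives 0.794)
- 18 or more of 60 (0.832; 17 gives 0.751)

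Do not apply this to escalation groups of 3, where BOIN already acts per dose.

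The cost is protocol wording and some extra meetings. Over the three checks, the probability of at least one firing is 0.2%, 12%, 35%, 65% and 97% at true rates of 10%, 20%, 25%, 30% and 40%. The 35% at exactly 25% is the main downside. Using the plain 25% counts instead (6, 11 and 16) would raise the first four figures to about 1%, 29%, 59% and 84%, which is why the 0.8 cut-off is preferable. A firing leads to a review, not a stop.

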#### 7.5.5. Post-Treatment Monitoring for Hematologic Second Primary Malignancy

Post treatment monitoring as clinically indicated will be performed for those subjects who 1) do not enroll in a new clinical study, 2) do not withdraw consent and 3) do not begin a new anti-neoplastic therapy. Monitoring will include a complete blood count with at least an automated differential or peripheral blood smear.

#### 7.5.6. Determination of Sample Size and Criteria for Early Stopping Due to Futility

This is a FIH study. The objective of this study is to evaluate the safety, tolerability, and PK of EZM0414 in order to determine MTD in Phase 1 part, and safety, tolerability, PK, and efficacy to determine RP2D in Phase 1b part.

This is an open-label study and there will be no randomization. Subjects will be enrolled based on their conditions.

The sample size of Phase 1 part is determined based on number of doses to be tested using BOIN design and there is no formal sample size estimation for the Phase 1b part of the study.

The study will enroll approximately 96 subjects, of which up to 36 subjects will be enrolled in Phase 1 dose escalation part and 60 subjects (20 subjects/cohorts) will be enrolled in Phase 1b dose expansion part. There will be 6 dose levels (starting at 100 mg, then 200 mg, 300 mg, 400 mg, 600 mg, and 900 mg) as well as an optional step-down dose level of 75 mg (if needed) to be tested in Phase 1 dose escalation part to determine MTD, and additional daily dose levels and/or dosing schedules (including BID regimen) may be studied based on clinical and pharmacokinetic data obtained during this study. The sample size will therefore be adjusted accordingly. There will be 3 cohorts for the dose expansion part: 20 R/R MM subjects with t(4;14), 20 R/R MM subjects without t(4;14) and 20 R/R DLBCL subjects.

The subjects who are treated at MTD in Phase 1 dose escalation part and do not experience any DLT will continue to receive the treatment beyond cycle 1 (be rolled over to the dose expansion part) until disease progression, occurrence of unacceptable toxicity, or withdrawal of consent, or need for treatment prohibited on this study.

There will be 3 looks performed in Phase 1b part when the data of 10, 15, and 20 subjects of a cohort have been available. The cohort will be terminated earlier if deemed futile by SRC and the study team.

## **7.6. Criteria for Study Termination**

The Sponsor reserves the right to discontinue the study for medical reasons or for any other reason at any time. If the study is prematurely terminated or suspended, the Sponsor will promptly inform the Investigators/institutions and the regulatory authority(ies) of the termination or suspension and the reason(s) for the termination or suspension. The institutional review board (IRB)/independent ethics committee (IEC) should also be informed promptly and provided with the reason(s) for the termination or suspension by the Sponsor or by the Investigator/institution, as specified by the applicable regulatory requirement(s).

The Investigator reserves the right to discontinue the study should his/her judgment so dictate. If the Investigator terminates or suspends a trial without prior agreement of the Sponsor, the Investigator should inform the institution where applicable, and the Investigator/institution should promptly inform the Sponsor and the IRB/IEC and should provide the Sponsor and the IRB/IEC with a detailed written explanation of the termination or suspension. Study records must be retained as noted in Section 18.3.

**Table 8: Schedule of Assessments for Dose Escalation and Dose Expansion**

Assessment	Screening	Cycle 1							Cycle 2				Cycle 3 and Cycle 4		Cycle 5+	EOT a	Safety Follow up b
Study day (window)	-28 to -1	1 c	2	3	4	8 (±3D)	15 (±3D)	22 (±3D)	1 (±3D)	2	8 (±3D)	15 (±3D)	1 (±3D)	15 (±3D)	1 (±3D)		30 (±3D)
Informed Consent	X																
Eligibility Criteria	X	X															
Demographics	X																
Medical History	X																
Physical Exam (Complete)	X	X														X	X
Physical Exam (Symptom-directed)						X	X	X	X			X	X	X	X		
Height (screening only) and body weight	X	X							X				X		X	X	X
Vital Signs	X	X	X	X d	X d	X	X	X	X	X	X	X	X	X	X	X	X
ECOG	X	X							X				X		X	X	X
12-lead ECG e	X	X	X			X	X	X	X	X	X	X	X		X e	X	
Disease assessment for DLBCL subjects f	X												C3 only		Cycle 5, 7, 9 etc	X	
Adverse Events									X								

Assessment	Screening	Cycle 1							Cycle 2				Cycle 3 and Cycle 4		Cycle 5+	EOT a	Safety Follow up b
Study day (window)	-28 to -1	1 c	2	3	4	8 (±3D)	15 (±3D)	22 (±3D)	1 (±3D)	2	8 (±3D)	15 (±3D)	1 (±3D)	15 (±3D)	1 (±3D)		30 (±3D)
Concomitant medications		X															
Hematology g *	X	X				X	X	X	X		X	X	X	X	X	X	
Blood chemistry h	X	X				X	X	X	X		X	X	X	X	X	X	
Coagulation test i	X	X				X	X	X	X		X	X	X	X	X	X	
Pregnancy test j	X	X						X				X		X	X	X	
Urinalysis	X	X						X				X		X	X	X	
EZM0414 oral administration		Continuous oral administration in 28-day cycles per escalation schedule or expansion. In dose escalation: EZM0414 will be administered on C1D1 but will not be administered on C1D2 and C1D3. C1D4, C1D15 and C2D2 dose will be administered after PK sample collection. In dose expansion: C1D2 and C2D2 dose will be administered after PK sample collection.															
Bone marrow aspirates and bone marrow biopsy k	X l	X l											X m		X m		
Serum β2 microglobulin (MM subjects only)	X															X	
Serum M-protein serum (MM only)	X	X							X				X		X	X	
24-hour urine sample for M-	X	X							X				X		X	X	

Assessment	Screening	Cycle 1							Cycle 2				Cycle 3 and Cycle 4		Cycle 5+	EOT a	Safety Follow up b
Study day (window)	-28 to -1	1 c	2	3	4	8 (±3D)	15 (±3D)	22 (±3D)	1 (±3D)	2	8 (±3D)	15 (±3D)	1 (±3D)	15 (±3D)	1 (±3D)		30 (±3D)
protein (MM only)																	
Serum free light-chain assay (MM only)	X	X							X				X		X	X	
MM Disease assessment by IMWG		X							X				X		X	X	
Skeletal survey (MM only) n	X	As clinically indicated and per the local standard of care for imaging (X-ray or MRI). The same methodology used at Screening should be used throughout the study for comparison purposes.															
CT or PET/CT for extramedullary soft tissue plasmacytoma (MM only)	X												X (Cycle 3 only)		X o		
Whole blood for exploratory analysis p		X					X		X				X		X		
Tumor tissue (DLBCL only) q	X	X											X (cycle 3 only)		X (optional)		
PK		Please refer to Table 9 for dose escalation PK and Table 10 for dose expansion PK collection schedule												X			
Abbreviations: aPTT = activated partial thromboplastin; BNP = brain natriuretic peptide; C = Cycle; CR = complete response; CT = computed tomography; D = Day; DLBCL = diffuse large B cell lymphoma; ECG = electrocardiogram; ECOG = Eastern Cooperative Oncology Group status; EOT = end of treatment; FDG = fluorodeoxyglucose; IMWG = International Myeloma Working Group; INR = international normalized ratio; MM = multiple myeloma; M-protein =																	

Assessment	Screening	Cycle 1							Cycle 2				Cycle 3 and Cycle 4		Cycle 5+	EOT a	Safety Follow up b
Study day (window)	-28 to -1	1 c	2	3	4	8 (±3D)	15 (±3D)	22 (±3D)	1 (±3D)	2	8 (±3D)	15 (±3D)	1 (±3D)	15 (±3D)	1 (±3D)		30 (±3D)

monoclonal protein; PK = pharmacokinetics; PT = prothrombin time; sCR = stringent complete response complete response; VGPR = very good partial response

a End of treatment visit should be completed within 7 days of the last dose of study drug. This visit may be completed at a scheduled visit when a decision to discontinue treatment is made.

b 30-day safety follow-up should be completed 30 (±3) days after last dose of study drug or before start of a new anti-cancer therapy, whichever occurs first.

c Cycle 1 Day 1 hematology, serum chemistries, coagulation and urinalysis may be performed on Cycle 1 Day -1.

d Only in Part 1 dose escalation.

e Collect single ECG at screening and triplicate ECGs at all other timepoints. ECGs during Cycle 1 and Cycle 2 are per [Table 9](#) (dose escalation) and [Table 10](#) (dose expansion). Triplicate ECGs will also be collected at pre-dose (within 30 min of dose) and 2-hours post (± 10min) on Day 1 of every odd cycle starting at Cycle 3 Day 1, and at end of treatment.

f Radiologic disease assessments at screening and every 8 weeks ±7 days. PET/CT whole body for FDG avid disease OR contrast enhanced CT of neck, chest, abdomen, and pelvis for subjects with non-FDG avid disease. Use the same modality for disease assessment through the study for each patient.

g Hematology assessments will include red blood cell count, hemoglobin, hematocrit, mean corpuscular volume, mean corpuscular hemoglobin, mean corpuscular hemoglobin concentration, white blood cell count with differential, platelet count, peripheral blood smear, and reticulocyte count.

\* Post treatment monitoring as clinically indicated will be performed for those subjects who 1) do not enroll in a new clinical study, 2) do not withdraw consent and 3) do not begin a new anti-neoplastic therapy. Monitoring will include a complete blood count with at least an automated differential or peripheral blood smear.

h Blood chemistry assessments will include sodium, potassium, blood urea nitrogen, aspartate aminotransferase, alanine aminotransferase, alkaline phosphatase, albumin, calcium, glucose, total creatine kinase, total bilirubin, lactic dehydrogenase, creatinine, total protein, bicarbonate, phosphorus, magnesium, uric acid, amylase, lipase, cardiac markers- BNP, and Troponin.

i Coagulation tests include aPTT, PT/INR, and fibrinogen.

j Serum pregnancy test at screening and serum/urine pregnancy test at all other visits. Cycle 1 Day 1 pregnancy test does not need to be repeated if screening test performed within 72 hours of Cycle 1 Day 1.

k Subjects with MM: Bone marrow aspirations and a bone marrow biopsy will be taken at screening/baseline (pre-dose), Cycle 3 Day 1, VGPR for translational studies. Bone marrow aspirates and bone marrow biopsies will be taken at CR and sCR to assess response according to IMWG 2016 criteria as per local institutional practice. If a SOC bone marrow will be performed a bone marrow aspiration will be taken for research in subjects with MM. A non-mandatory bone marrow biopsy and bone marrow aspirates can be taken at progression for research.

l MM: Bone marrow aspirates and bone marrow biopsy are taken either at screening/baseline or at Cycle 1 Day1 (predose).

m Translational research samples will be collected at Cycle 3 Day 1, VGPR and progression. A bone marrow aspirate will be collected for research if SOC biopsy will be performed for CR or sCR for MM. SOC samples will be taken at CR and sCR to assess ORR.

n Skeletal surveys for sites that do not have CT/PET-CT capabilities.

o Perform CT or PET/CT at screening, Cycle 3 Day 1 (±7 days) and then starting at cycle 6, every 3 cycles (±7 days) or sooner if clinically indicated.

p Whole blood will be collected for: Plasma and CTC in the PBMC fraction, PBMCs and/or buffy coat at Cycle 1 Day1 (pre-dose), Cycle 1 Day 15 (pre-dose), Cycle 2 Day 1 (pre-dose), Cycle 3 Day 1 (pre-dose), progression, or any response. After Cycle 3 Day 1 every other cycle until Cycle 26 and then every 4 Cycles after Cycle 26. For exact sample collections see quick chart (Laboratory manual).

q DLBCL subjects: Archival tissue or an optional fresh biopsy can be taken in subjects with DLBCL. An optional biopsy can be taken at PR. A non-mandatory biopsy can be taken at progression. An optional biopsy can be taken on-treatment at Cycle 3 Day 1.

Subjects with DLBCL: Bone marrow biopsy at suspected complete response if bone marrow status was unknown or positive at study entry. Bone marrow aspirate will be taken at CR if at baseline bone marrow status was unknown or positive.

